**Title:** Diagnostic Accuracy of Artificial Intelligence, CBCT, and Clinical Examination in Detecting Number of Root Canals in Conventional and Retreated Maxillary and Mandibular Molars

NCT Number: "Pending"

Date: 29/10/2024

Introduction: Accurate root canal detection is crucial for successful endodontic treatment, particularly in complex molar cases. Conventional methods, such as clinical examination and cone-beam computed tomography (CBCT), have their limitations, as high radiation exposure. Recent advancements in Artificial Intelligence (AI) have shown promise in improving diagnostic accuracy. This study aims to compare the effectiveness of AI, CBCT, and clinical examination using a dental operating microscope (DOM) in detecting root canals in upper first, upper second, and lower first molars, in both conventional and retreatment cases.

Methods: CBCT scans from 210 patients requiring non-surgical root canal therapy or re-treatment were selected. The scans were analyzed using three detection methods: clinical examination via DOM, interpretation by two experienced endodontists using CBCT, and an AI convolutional neural network (CNN) software (Diagnocat). The detected number of root canals was recorded and compared across the three methods. Statistical analysis was performed to evaluate the diagnostic accuracy, including sensitivity, specificity, and agreement between methods.

Results: AI detected a significantly higher number of molars with three or four canals compared to clinical examination and CBCT in conventional treatment cases (P < 0.001). In retreatment cases, AI demonstrated a similar trend, with one case of five root canals detected clinically but missed by both CBCT and AI. Overall, AI showed higher diagnostic accuracy (88.2%) compared to clinical examination and CBCT. There was no significant difference in AI accuracy between molar types, though the upper first molar had the highest accuracy (93.9%).

Conclusion: AI demonstrated higher accuracy in detecting root canals compared to CBCT and clinical examination in both conventional and retreatment cases, particularly in upper molars. These findings highlight the potential of AI as a valuable tool for enhancing diagnostic precision in endodontics, especially in complex cases. However, further research is necessary to address the limitations of AI

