# **Study Objectives and Hypotheses**

• **Objective**: To evaluate and compare the accuracy of AI, CBCT, and clinical examination in detecting the number of root canals in maxillary and mandibular molars.

• **Hypothesis**: AI will demonstrate superior diagnostic accuracy compared to CBCT and clinical examination.

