## **Study Design**

- Sample Size: 212 molars.
- Randomization: Not applicable (observational study).
- **Blinding**: Independent assessment by two experienced endodontists for CBCT and clinical examination.
- Control Group: Not applicable.

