#### **Study Procedures**

- CBCT scans are analyzed by endodontists and AI software (Diagnocat).
- Clinical examination is performed using a dental operating microscope (DOM).
- The detected number of canals is recorded and compared across methods.
- Statistical analysis is performed to evaluate accuracy.

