Title: Diagnostic Accuracy of Artificial Intelligence, CBCT, and Clinical Examination in Detecting Number of Root Canals in Conventional and Retreated Maxillary and Mandibular Molars

NCT Number: “Pending”

Date: 29/10/2024

Statistical Analysis

Qualitative data were presented as frequencies and percentages. Friedman's test was used to compare between number of canals detected by the three methods. Kappastatistic was used to assess agreement between the threemethods. Kappa values ranging from 0.6 to 0.8 indicate good agreement while values ranging from 0.8 to 0.99 indicate very good agreement. Numerical data were explored for normality by checking the distribution of data and using tests of normality (Kolmogorov-Smirnov and Shapiro-Wilk tests). All data showed normal (parametric) distribution except for length of canal division from the apex and percentage of canal unity data which showed non-normal (non-parametric) distribution. Data were presented as mean, standard deviation (SD), median and range values. For parametric data, Student's t-test was used to compare between correctly and incorrectly diagnosedcases. For non-parametric data, MannWhitney U was used to compare between correctly and incorrectly diagnosed cases. Binary logistic regression model was constructed using diagnosis (Correct/Incorrect) as the dependent variable. Treatment, molar type, inter-orifice distance, percentage of canal unity and Vertucci classification were the independent variables. The significance level was set at $P \leq 0.05$. Statistical analysis was performed with IBM SPSS Statistics for Windows, Version 23.0. Armonk, NY: IBM Corp. ROC (Receiver Operating Characteristic) curve was constructed to determine the diagnostic accuracy measures of AI in relation to CBCT. Comparison between areas under the ROC curve (AUC) were performed using z-test. ROC curve analysis was performed with MedCalc® Statistical Software version 19.5.1 (MedCalc Software Ltd, Ostend, Belgium; <https://www.medcalc.org>; 2020)

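### No reference standard outside the three methods is named, so as specified the plan does not support the hypothesis that AI is more accurate than both CBCT and clinical examination

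*SAP*

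**What the plan says.** The protocol (Study Objectives and Hypotheses) states one hypothesis: "AI will demonstrate superior diagnostic accuracy compared to CBCT and clinical examination". Its opening summary, under Methods, adds: "Statistical analysis was performed to evaluate the diagnostic accuracy, including sensitivity, specificity, and agreement between methods". Sensitivity and specificity need a reference; the summary does not give one. Under Study Procedures, the endodontists and the AI software both work from the CBCT images, while the clinical count comes from the dental operating microscope (DOM).

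The SAP (Statistical Analysis) provides:

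- Friedman's test on the canal counts from the three methods.
- Kappa for agreement between them.
- A ROC analysis to "determine the diagnostic accuracy measures of AI in relation to CBCT".
- An AUC comparison: "Comparison between areas under the ROC curve (AUC) were performed using z-test". Which curves are compared is not stated.
- Analyses of correctly against incorrectly diagnosed cases by t-test and Mann-Whitney test, and a regression: "Binary logistic regression model was constructed using diagnosis (Correct/Incorrect) as the dependent variable". Neither whose diagnosis this is nor what makes it correct is stated.

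The ROC item in the protocol's own Statistical Analysis Plan section names no reference. The opening summary nevertheless reports AI accuracy of 88.2% and concludes that AI is more accurate than both other methods.

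**The concern.** A claim that one method is more accurate than two others needs a standard against which all three can be wrong. The documents name none. If one of the three methods fills that role, it cannot be beaten on its own terms, and at least half of the hypothesis becomes untestable.

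This is the study's only stated hypothesis and its headline conclusion. The reported excess of molars in which AI found three or four canals could mean more true canals or more false ones, and the planned analyses cannot tell these apart. With CBCT as the reference, a tooth that AI reads correctly and CBCT misreads is scored as an AI error. An error that both make on the same scan is scored as an AI success.

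**Working it through.** **Inputs.** N = 212 molars (protocol, Study Design: "Sample Size: 212 molars"); 210 patients (opening summary, Methods); AI accuracy 88.2% (opening summary, Results). No numerator, cross-table or sample-size derivation is given.

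**Step 1: reproduce 88.2%.** 187/212 = 88.21%, which rounds to 88.2%. The neighbours do not fit: 186/212 = 87.74% and 188/212 = 88.68%. With 210 as denominator nothing fits: 185/210 = 88.10% and 186/210 = 88.57%. The figure is therefore consistent with 187 of 212 molars. The 187 is inferred, and the match does not show which reference was used.

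**Step 2: take each method as the reference.** A method scored against itself has accuracy N/N = 100% (AUC 1).

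| Reference | Fixed at 100% | Consequence for the hypothesis |
|---|---|---|
| CBCT | CBCT | AI minus CBCT is at most 0 |
| DOM count | Clinical examination | AI minus clinical examination is at most 0 |
| AI | AI | Superiority is assumed, not tested |
| None (CBCT is only a comparator) | – | Accuracy is undefined until a reference is named |

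If 88.2% was scored against CBCT or against DOM, that method stands at 100% and AI is 88.2 - 100 = -11.8 points from it. The figure then cannot be higher than both.

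**Step 3: what 88.2% against CBCT says about true accuracy.** Take 187 agreements and 212 - 187 = 25 disagreements. Assume that agreements are correct and that exactly one method is right in each disagreement. Let x be the number of disagreements in which AI is right.

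- True AI accuracy = (187 + x)/212
- True CBCT accuracy = (187 + 25 - x)/212
- Difference = (2x - 25)/212

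| x | AI | CBCT | AI minus CBCT |
|---|---|---|---|
| 0 | 88.2% | 100% | -11.8 points |
| 12 | 93.9% | 94.3% | -0.5 points |
| 13 | 94.3% | 93.9% | +0.5 points |
| 25 | 100% | 88.2% | +11.8 points |

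The same agreement figure fits opposite truths.

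**Step 4: can the other analyses fill the gap?** Friedman's test asks whether the counts differ, not which count is right. Kappa measures agreement and needs no truth standard. The Correct/Incorrect analyses do concern accuracy, but they look for predictors of correctness, do not compare methods, and have no stated reference. The z-test might compare molar types, since the opening summary reports that "There was no significant difference in AI accuracy between molar types"; that is an inference, and such a comparison would not address the hypothesis.

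**The case against.** The best reply is that an unstated reference is not an absent one. A Correct/Incorrect outcome implies that some standard was applied, and the AUC z-test could have compared AI with CBCT against it. The opening summary also describes one five-canal tooth as found clinically and missed by the other two methods, which hints that the clinical count was treated as true. If CBCT is meant only as the comparator, the fault is an omission that one sentence could repair.

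Much of this stands, and it limits the point in three ways.

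- A reader might infer that AI superiority can never be shown in this study. The documents do not support that: they establish that no independent reference is specified, not that none existed.
- A reader might take the ROC curve to be the only analysis that touches accuracy. It gives the only stated accuracy measures, but the Correct/Incorrect analyses touch accuracy too.
- A reader might put a fixed bias on each misread tooth. The SAP plans no AI-minus-CBCT difference to which such a bias would apply, the number of such teeth is not given, and both methods can be wrong with different counts.

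The hint of a clinical reference does not rescue the hypothesis. With DOM as the reference, AI can be compared with CBCT but cannot be shown superior to clinical examination. Without a declared reference, the five-canal tooth shows only that the methods disagreed.

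**Conclusion.** The point holds and should be fixed before any superiority claim is made. As specified, the plan does not support superiority of AI over both CBCT and clinical examination. That part is structural and needs no data: whichever of the two is the reference stands at 100%, and AI can at best tie with it.

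The range in Step 3 is conditional. It assumes that 88.2% was scored against CBCT on 212 molars, that the numerator is 187, that agreements are correct, and that exactly one method is right in each disagreement. Under those assumptions the data leave the sign open. The range is not an estimate of the error in this study, and no corrected accuracy can be computed, because no counts against an independent reference are reported.

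**What to change.** In the SAP, name the one reference used for the ROC analysis and for Correct/Incorrect in the t-tests, Mann-Whitney tests and logistic regression. State which AUCs the z-test compares. Limit accuracy claims to methods that are not that reference. If a reference independent of all three methods was used, name it, and define Correct/Incorrect and paired comparisons of AI with CBCT and AI with clinical examination by it. If not, choose one of these:

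- **(a) CBCT stays the reference.** Report AI's results as agreement with CBCT and withdraw superiority over both CBCT and clinical examination. The second withdrawal is needed because the stated ROC analysis covers AI only, and scoring DOM against CBCT would favour AI, which reads the same scans.
- **(b) The recorded DOM count becomes the reference.** Score AI and CBCT per tooth against it, with a paired comparison and 95% CI, labelled post hoc. Note that a canal missed under DOM counts as an imaging error. Report comparisons with DOM as agreement, and withdraw superiority over clinical examination.
- **(c) No reference is accepted.** Restrict all conclusions to agreement and canal counts.

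The cost is rewording of the SAP, hypothesis and conclusions and, for (b), a re-analysis of counts already recorded. No new patients or scans are needed. The real price is a narrower claim: unless an independent reference was used, at least half of the hypothesis goes. Under (b) the AI-CBCT result also rests on an imperfect reference. That may count against AI, which is reported to find more three- and four-canal molars than clinical examination.
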